8.6 Halting Rules

8.6.1 Dose Escalation Halting Criteria

If either of the following criteria is met, escalation to the next planned dose cohort will not proceed until all available study data have been reviewed by the SMC.

- Two or more subjects in the same cohort experience a Grade 2 related AE (laboratory or systemic) that is attributed to the study drug and coded under the same high-level term per the Medical Dictionary for Regulatory Activities coding, throughout the duration of the study.
- Two or more subjects in the same cohort experience a Grade 3 AE (laboratory or systemic) that is coded under the same high-level term per the Medical Dictionary for Regulatory Activities coding, regardless of causality assessment by the Investigator, throughout the duration of the study.

If dose escalation is halted, the study may resume if deemed acceptable by the SMC following review of all available study data.

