8.1.1.1 Adverse Events Grading

All AEs (laboratory and clinical symptoms) will be graded for severity and assessed for relationship to the IP (see definitions below). Adverse events characterized as intermittent require documentation of onset and duration of each episode. The start and stop date of each reported AE will be recorded on the appropriate data collection form and eCRF. Changes in the severity of an AE will be documented to allow an assessment of the duration of the event at each level of intensity.

Severity of Event: Adverse events will be assessed by the Investigator using a protocol-defined grading system (toxicity table included in Section 17.2). For events not included in the protocol-defined grading system, the following guidelines will be used to quantify severity:

- Mild (Grade 1): Events that are transient and may require only minimal or no treatment or therapeutic intervention and do not interfere with the subject's usual activities of daily living.
- Moderate (Grade 2): Events that are alleviated with additional specific therapeutic intervention. The event interferes with usual activities of daily living, causing discomfort but poses no significant or permanent risk of harm to the subject.
- Severe (Grade 3): Events interrupt usual activities of daily living, or significantly affects clinical status, or may require intensive therapeutic intervention. Severe events are usually incapacitating.

Relationship to Investigational Product: The assessment of the AE's relationship to the IP will be done by the licensed study physician indicated on Form FDA 1572 and the assessment will be part of the documentation process. Whether the AE is related or not, is not a factor in determining what is or is not reported in this study. If there is any doubt as to whether a clinical observation is an AE, the event should be reported.

In a clinical trial, the IP must always be suspect. The relationship to the IP will be assessed for AEs using the terms related or not related:

- Related There is a reasonable possibility that the IP caused the AE. Reasonable possibility means that there is evidence to suggest a causal relationship between the IP and the AE.
- Not Related There is not a reasonable possibility that the administration of the IP caused the event.

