8.2.2 Dose Escalation Criteria

This study is designed such that dose escalation is allowed only after a blinded safety data review of each cohort by the SRC has occurred as outlined in Section 8.7.1. Study assessments (eg, AEs, clinical laboratory test results, vital sign measurements, and 12-lead ECG results) will be used to evaluate safety of a given dose level. Dose escalation will be dependent on review of the safety data. Clinically significant results will be discussed with the Sponsor before dose escalation continues. Data from a minimum of 6 subjects dosed per cohort must be reviewed before each dose escalation.

Based on the review of safety data and recommendations by the SRC, SMC, or both, the Sponsor and the Investigator may choose to repeat a dose level, administer a dose less than the previous dose, escalate to a dose lower than the next planned dose, or prolong the duration of the infusion. Before implementing any change, the IRB will be notified and provided with the rationale for approval.

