8.4 Type and Duration of Follow-up of Subjects after Adverse Events

Adverse events will be assessed and followed from initial recognition of the AE through resolution even if the duration of follow-up goes beyond the final follow-up visit.

Serious AEs will be followed through resolution even if duration of follow-up goes beyond the final follow-up visit.

Resolution of an AE is defined as the return to pretreatment status or stabilization of the condition with the expectation that it will remain chronic.

8.5 Procedures to be Followed in the Event of Abnormal Laboratory Test Values or Abnormal Clinical Findings

Results of laboratory values collected during the conduct of the study will be reviewed by the Investigator or designee within 24 hours of receipt at the clinical site. As this study will be conducted in healthy subjects, assessment of laboratory abnormalities will be performed in accordance with the grading scale provided in Section 17.2, which is adapted from the FDA guideline, "Toxicity Grading Scale for Healthy Adult and Adolescent Volunteers Enrolled in Preventive Vaccine Clinical Trials" (DHHS 2007). The adaptation is applied to account for local laboratory normal values and for compliance with the Clinical Data Interchange Standards Consortium. Any findings meeting Grade 3 criteria must be repeated immediately to rule out spurious values. All abnormal laboratory test values and findings on physical examination will be included in the study data and summarized in the safety analyses as described in Section 10.4.5. Any treatment-emergent AEs that are appropriately graded according to the toxicity scale in Section 17.2 will be captured as AEs in the eCRF.

Abnormal laboratory values occurring during the study will be followed until repeat test results return to normal, stabilize, or a cause is identified. If the laboratory abnormality is identified at the final scheduled visit, the subject will be requested to return for additional testing.

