8.6.2 Halting Criteria for Subject Infusions

The Investigator and study site staff must carefully observe the subjects for any AE during the infusion.

The infusion will be halted for an individual subject and will not resume if any of the following manifestations occur during the 1-hour infusion:

- Occurrence during dosing that, in the opinion of the Investigator, results in the inability to have confidence that the intended dose of IP was delivered.
- Infusion-related reaction of Grade 2 or higher.

In case of a suspected infusion-related reaction, at the discretion of the Investigator, the infusion rate may be slowed from a rate of 250 mL/hour to a rate of 125 mL/hour for symptom management. The infusion may also be stopped. The subject will be observed to determine the severity of the reaction for a period of up to 15 minutes. Depending on the assessment of the subject, supportive care can be administered, and the infusion may permanently be stopped. If the Investigator determines that there is no infusion reaction, no ongoing supportive care is required after dosing is stopped, or if the symptoms of the clinical reaction have been improved after 15 minutes, the infusion may be restarted. The decision to

continue the infusion is based on the assessment by the Investigator. The infusion will be halted if there is a reoccurrence after a pause in dosing.

- Symptomatic low blood pressure of <90 mm Hg systolic or >30% decrease from baseline in systolic or diastolic blood pressure at predose.
- Confirmed tachycardia with an increase in resting heat rate to ≥130 beats per minute (bpm), or development of ventricular dysrhythmia, or bradycardia (<45 bpm, or <40 bpm in subjects with baseline of <60 bpm) associated with complaints of dizziness, nausea, or feeling faint.
- Syncope.
- Confusion.
- Suspected Grade 3 AE or SAE.

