10.1.3. Severity of Adverse Event

All AEs (laboratory and clinical symptoms) will be graded for severity. The severity will be classified as mild, moderate, or severe using the following criteria:

- Mild (Grade 1): Events that are transient and may require only minimal or no treatment or therapeutic intervention and do not interfere with the subject's usual activities of daily living.
- Moderate (Grade 2): Events that are alleviated with additional specific therapeutic intervention. The event interferes with usual activities of daily living, causing discomfort but poses no significant or permanent risk of harm to the subject.
- Severe (Grade 3): Events interrupt usual activities of daily living, or significantly affects clinical status, or may require intensive therapeutic intervention. Severe events are usually incapacitating.

All TEAEs will be summarized for each treatment group and total by maximum severity. If the severity information is missing, the AE will be considered severe in the summary but will be presented as missing in the data listings.

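### Read literally at worst grade, Protocol 8.6.1 sends two related Grade 2 events to the SMC automatically but not one related Grade 2 plus one related non-serious, non-QTcF Grade 3

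*Protocol*

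**What the plan says.** Protocol 8.6.1 lists two criteria; meeting either one stops escalation until the SMC has reviewed all available data. The first applies when "Two or more subjects in the same cohort experience a Grade 2 related AE (laboratory or systemic) that is attributed to the study drug", with the events coded under one MedDRA high-level term. The second applies when at least two subjects in a cohort have a Grade 3 event under one high-level term, whatever the causality. Neither criterion adds the two grades together, and the section does not say how to count a subject whose event changes grade.

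The surrounding rules matter here:

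- Protocol 8.2.2: "dose escalation is allowed only after a blinded safety data review of each cohort by the SRC has occurred", and "Clinically significant results will be discussed with the Sponsor before dose escalation continues".
- Protocol 8.5, for laboratory and clinical findings: "Any findings meeting Grade 3 criteria must be repeated immediately to rule out spurious values".
- Protocol 8.6.2, on stopping an individual infusion, lists "Infusion-related reaction of Grade 2 or higher".
- Protocol 8.6.3 halts dosing for, among other things, one related SAE, one life-threatening hypersensitivity reaction, one confirmed Grade 3 QTcF, or related Grade 3 events in two subjects within a system organ class.
- Protocol 8.7.2 adds SMC review when an SAE occurs, at the Sponsor's request, and at time points set in a charter that is not among the documents.

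**The concern.** A halting rule should not become less demanding as the events become more severe. Take two related Grade 2 events in one cohort and make one of them worse: on a literal worst-grade reading the mandatory SMC hold disappears.

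ALT, one of the tests Protocol 7.2.1 uses for escalation decisions, shows this. Table 17-3 puts Grade 2 at 2.6 to 5.0 times the upper limit of normal and Grade 3 above 5.0 times. Two related rises to 4 times the limit, coded to one high-level term, require SMC review. One rise to 4 times and one to 6 times, both related and neither serious, do not.

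This is a first-in-human study whose next step is a dose two to three times higher (30, 90, 250, 500, 1000 mg). What is at stake is whether an independent committee, which may see data by arm, looks at the worse pattern by rule or only if someone decides to ask.

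**Working it through.** The plan states no trigger probability for its halting rules, so there is no figure to reproduce. The check has three steps.

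**1. Which patterns trigger 8.6.1.** Let n2 and n3 be the numbers of subjects in one cohort whose worst related event in one high-level term is Grade 2 or Grade 3. Take the Grade 3 events as non-serious and not QTcF. As written, the rule is n2 ≥ 2 or n3 ≥ 2. With Grade 2 as a floor it is n2 + n3 ≥ 2 (two related Grade 3 events also meet this).

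| n2, n3 | As written | Grade 2 as a floor |
|---|---|---|
| 2, 0 | SMC review | SMC review |
| 1, 1 | none | SMC review |
| 0, 2 | SMC review | SMC review |
| 2, 1 or 1, 2 | SMC review | SMC review |
| 1, 0 or 0, 1 | none | none |

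Only the exact pair (1, 1) differs.

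**2. Whether another rule picks up that pair.** A single related Grade 3 does not meet the 8.6.3 system-organ-class rule, which needs a second such subject. The SAE and QTcF rules are excluded by construction, and a life-threatening reaction would be an SAE. What remains is a separate event that meets some trigger (for example a second related Grade 3 in the same system organ class, or an SAE in another subject), a charter-defined SMC review, or the Sponsor's request under 8.7.2. None of these follows from the pair itself. Under 8.7.1 the safety review committee (SRC) tells the Sponsor that the next cohort can start when no listed event has occurred.

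**3. How often the pair might occur.** Cohort size comes from Protocol 10.2: 6 AV-1 and 2 placebo. The event rates are assumptions; the documents give none, and Protocol 2.2.2 expects no drug-related toxicity. Let a and b be the per-subject probabilities that the worst related event in one high-level term is Grade 2 or Grade 3, let c = 1 − a − b, and take subjects as independent. Then

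P(1, 1) = n(n − 1) · a · b · c^(n − 2).

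For n = 6:

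- 5%/2%: 30 × 0.05 × 0.02 × 0.93^4 = 0.0224
- 10%/5%: 30 × 0.10 × 0.05 × 0.85^4 = 0.0783
- 20%/10%: 30 × 0.20 × 0.10 × 0.70^4 = 0.1441

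For n = 8, all dosed subjects at the same rates:

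- 5%/2%: 56 × 0.05 × 0.02 × 0.93^6 = 0.0362
- 10%/5%: 56 × 0.10 × 0.05 × 0.85^6 = 0.1056
- 20%/10%: 56 × 0.20 × 0.10 × 0.70^6 = 0.1318

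The trigger probability of the whole rule, from the trinomial distribution, agrees. With p = a + b, the floor version equals 1 − (1 − p)^n − np(1 − p)^(n − 1).

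| Rates | n = 6, as written → floor | n = 8, as written → floor |
|---|---|---|
| 5%/2% | 3.84% → 6.08% | 6.72% → 10.35% |
| 10%/5% | 14.52% → 22.35% | 23.72% → 34.28% |
| 20%/10% | 43.58% → 57.98% | 61.29% → 74.47% |

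Within rounding, each difference is the probability of the (1, 1) pair. Both cohort sizes are shown because 8.6.1 counts subjects in the cohort and causality is judged blind, so a placebo subject can contribute. The 6-subject figures therefore do not bound the rule as written. No deduction is made for other triggers: that would need Grade 3 rates for a whole system organ class, which the documents do not give.

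**The case against.** The strongest reply is that the gap depends on a counting rule that 8.6.1 does not contain. Protocol 8.1.1.1 states: "Changes in the severity of an AE will be documented to allow an assessment of the duration of the event". A subject who passed through Grade 2 on the way to or from Grade 3 has arguably experienced a Grade 2 event, and would meet the first criterion. The worst-grade convention appears only as a table rule in SAP 10.1.3 ("All TEAEs will be summarized for each treatment group and total by maximum severity"), which does not govern halting. Usage elsewhere also points to a floor: 8.6.3 defines a Grade 2 QTcF change as 480 msec or more, although Table 17-1 caps Grade 2 at 499 msec.

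This makes the gap dependent on the reading, but does not remove it. 8.6.1 does not adopt the any-grade-reached reading, and 8.6.2 shows that the explicit wording was available. Nor need a Grade 2 phase be on record in time. Escalation is decided on data through Day 8, and the only scheduled post-dose laboratory tests by then are at 48 hours and Day 8.

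A second reply is that the pair is narrow and other safeguards exist. That stands. Some Grade 3 definitions in Tables 17-1 and 17-4 involve medical intervention or hospitalization, so some such events would be judged serious and would trigger review alone. A reader might infer that escalation could follow the mixed pair without any review. The documents do not support this: blinded SRC review, Sponsor discussion of clinically significant results and repeat of Grade 3 findings are all required, the SRC includes the DMID Medical Monitor, and 10.3.3 allows a cohort to be unblinded to decide whether escalation ends. Nor is the SMC closed to the pair unless a further event occurs, because the Sponsor may refer it under 8.7.2. What is absent is automatic referral.

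**Conclusion.** The point holds in a limited form. If subjects are counted at worst grade and the text is read literally, exactly one related Grade 2 plus one related non-serious, non-QTcF Grade 3 in one cohort and high-level term forces no SMC review, while the milder two-Grade-2 pattern does. That conclusion follows from the wording and needs no rates.

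Its size is uncertain: roughly 2% to 14% per cohort and high-level term for 6 AV-1 subjects, or 4% to 13% for all 8, across the three assumed rate pairs and before other triggers are deducted. It would be tempting to read these as forecasts or as limits for this trial. They are neither, since every rate is illustrative.

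A reader might also infer that the sponsor chose a weaker rule for the worse pattern. The usage in 8.6.2 and 8.6.3 suggests instead that Grade 2 was meant as a floor. This is a small wording correction to a safety rule, worth making because 8.7.1 calls for objective escalation criteria.

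**What to change.** In the first criterion of Protocol 8.6.1, replace the bare grade with *a related AE of Grade 2 or higher*, keeping the cohort, attribution and high-level-term conditions. Leave the second criterion unchanged: it still covers Grade 3 events judged unrelated. Use the same wording in the SMC charter if it repeats the criteria.

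The cost is one phrase in a protocol amendment, plus occasional extra SMC reviews with escalation waiting for each. Relative to a literal worst-grade reading, the added reviews are the (1, 1) pairs calculated above, fewer where another trigger already applies. If the site already treats Grade 2 as a floor, there are none.

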8.6.2 Halting Criteria for Subject Infusions

The Investigator and study site staff must carefully observe the subjects for any AE during the infusion.

The infusion will be halted for an individual subject and will not resume if any of the following manifestations occur during the 1-hour infusion:

- Occurrence during dosing that, in the opinion of the Investigator, results in the inability to have confidence that the intended dose of IP was delivered.
- Infusion-related reaction of Grade 2 or higher.

In case of a suspected infusion-related reaction, at the discretion of the Investigator, the infusion rate may be slowed from a rate of 250 mL/hour to a rate of 125 mL/hour for symptom management. The infusion may also be stopped. The subject will be observed to determine the severity of the reaction for a period of up to 15 minutes. Depending on the assessment of the subject, supportive care can be administered, and the infusion may permanently be stopped. If the Investigator determines that there is no infusion reaction, no ongoing supportive care is required after dosing is stopped, or if the symptoms of the clinical reaction have been improved after 15 minutes, the infusion may be restarted. The decision to

continue the infusion is based on the assessment by the Investigator. The infusion will be halted if there is a reoccurrence after a pause in dosing.

- Symptomatic low blood pressure of <90 mm Hg systolic or >30% decrease from baseline in systolic or diastolic blood pressure at predose.
- Confirmed tachycardia with an increase in resting heat rate to ≥130 beats per minute (bpm), or development of ventricular dysrhythmia, or bradycardia (<45 bpm, or <40 bpm in subjects with baseline of <60 bpm) associated with complaints of dizziness, nausea, or feeling faint.
- Syncope.
- Confusion.
- Suspected Grade 3 AE or SAE.

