Mild transient reaction; infusion interruption not indicated; intervention not indicated.	Therapy or infusion interruption indicated but responds promptly to symptomatic treatment (eg, antihistamines, nonsteroidal anti-inflammatory drugs, narcotics [opioids], intravenous fluids); prophylactic medication indicated for less than or equal to 24 hours.	Prolonged (eg, not rapidly responsive to symptomatic medication and/or brief interruption of infusion); recurrence of symptoms following initial improvement; hospitalization indicated for other clinical sequelae.

Source: Adapted from the National Cancer Institute Common Terminology Criteria for Adverse Events (Version 5.0) for infusion-related reactions.

^{*}Only values above the ULN and below the LLN are considered abnormal.

^{**}For females: In case of menstruation, screening urinalysis must be postponed, but a result should be available prior to Day 1. Hematuria is acceptable for females in menses for the purposes of evaluating study halting criteria and dose escalation.

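### Section 8.6.2 of the protocol both forbids and permits restarting the infusion after a Grade 2 infusion-related reaction that improves within the observation period

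*Protocol*

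**What the plan says.** Protocol Section 8.6.2 sets the rule for stopping one subject's infusion. Its lead-in is mandatory: "The infusion will be halted for an individual subject and will not resume if any of the following manifestations occur during the 1-hour infusion". One of the bullets it governs is "Infusion-related reaction of Grade 2 or higher". A later bullet covers "Suspected Grade 3 AE or SAE".

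A paragraph of handling instructions sits directly under the infusion-reaction bullet. It applies to any suspected reaction, at the Investigator's discretion. It allows slowing or stopping the infusion, and then says "The subject will be observed to determine the severity of the reaction for a period of up to 15 minutes". Next it says that "supportive care can be administered, and the infusion may permanently be stopped". It then gives the conditions for restart: the Investigator finds no reaction, no continuing supportive care is needed once dosing has stopped, or, in its own words, "if the symptoms of the clinical reaction have been improved after 15 minutes, the infusion may be restarted". It ends by requiring a halt if the reaction comes back after a pause.

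Section 6 says infusion-related events are graded on the scales in Section 17.2. Table 17-4 in that section is the relevant scale, and SAP Appendix 3 reproduces it. Grade 1 is a mild, passing reaction with "infusion interruption not indicated; intervention not indicated". Grade 2 is a reaction for which therapy or interruption is indicated and which responds promptly to symptomatic treatment. Grade 3 includes reactions that are prolonged or that return after first improving.

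**The concern.** The bullet and the paragraph beneath it appear to give different orders for the same subject. The lead-in says the infusion stays off once the reaction is Grade 2. The paragraph says permanent stopping is something the Investigator *may* choose, and that improvement at 15 minutes is enough to restart. The paragraph names no grade above which restart is barred.

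AV-1 has not been given to humans before, and this rule protects a healthy volunteer while the infusion is running. If both orders stand, two physicians could treat the same reaction in opposite ways and each could point to Section 8.6.2. The choice also decides whether the subject receives the rest of the dose. That affects the PK analysis, because the PK population requires the full dose of AV-1 (Protocol Section 10.4.1; SAP Section 4.2).

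**Working it through.** No arithmetic settles this. The check is to take each possible outcome of the observation period and read both parts of Section 8.6.2 against it, using the Table 17-4 grades and assuming that no other halting bullet is met at the same time.

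| Outcome of the pause | Lead-in and reaction bullet | Paragraph below the bullet | Do they conflict? |
|---|---|---|---|
| No infusion-related reaction | Not triggered | Restart allowed | No |
| Grade 1 | Not triggered | Restart allowed | No |
| Grade 2, symptoms improved after 15 minutes | Stop, no resumption | Restart allowed at the Investigator's discretion | Yes |
| Grade 3 | Stop, no resumption | No grade limit stated, but the separate suspected-Grade-3 bullet stops the infusion and has no restart text | No practical doubt |

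Three features of the text bear on the Grade 2 row.

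1. The absence of a reaction is already a restart condition of its own. The condition on improved symptoms must therefore cover a real clinical reaction.
2. The paragraph allows supportive care before it reaches the restart sentence. A reaction that needed such care and then improved does not fit Grade 1, which requires "infusion interruption not indicated; intervention not indicated". It does fit Grade 2.
3. Permanent stopping is expressed as a *may* under a lead-in that says *will not*.

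A pause does not by itself make a reaction Grade 2. Table 17-4 asks whether interruption was indicated, and an Investigator can pause as a precaution and later judge that it was not. That case ends in Grade 1 and raises no conflict.

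I looked for a sentence elsewhere that ranks the two instructions and found none. Section 5.2.1 lists meeting the individual halting criteria as a reason to stop a subject's participation, but it does not say how the restart text limits those criteria. Section 6 requires interrupted and partial infusions to be documented, but does not say when they may resume.

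**The case against.** The best defence is that the two texts have different triggers. The bullet concerns a reaction already graded 2 or higher. The paragraph concerns a suspected reaction not yet graded, and the observation period exists to determine severity. The order would be: suspect, slow or stop, grade, decide. Once the grade is 2, the mandatory lead-in governs, and the *may* clauses describe only the time before the grade is known. Section 5.2.1 fits this reading, since it treats the Section 8.6.2 items as halting criteria.

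Much of this stands. It is a plausible account of what was meant, and it is why I call the point a moderate-confidence inconsistency. It does not remove the problem. The limit to no reaction or Grade 1 is not written, and restart on improved symptoms, possibly after supportive care, sits badly with the Grade 1 definition.

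The defence is also right that harm is limited. A study physician is present at dosing (Section 6), and recurrence after a pause halts the infusion. Suspected Grade 3 events, syncope, confusion, symptomatic hypotension and marked heart-rate changes have their own stops. Section 8.6.1 counts related Grade 2 events toward the escalation halt whether or not the infusion was restarted.

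A reader might infer that a restart changes what counts toward the study-level halt in Section 8.6.3, because recurrence is Grade 3 in Table 17-4. The documents do not support that. The table does not make recurrence depend on a restart, so symptoms that return after a permanent stop are Grade 3 too. Nothing in the documents says how far restarting alters the chance of recurrence. One such event also triggers nothing under that criterion, which needs at least two subjects with related Grade 3 events in the same system organ class.

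**Conclusion.** Section 8.6.2 is internally inconsistent for one case: a Grade 2 infusion-related reaction that has improved after 15 minutes. It should be corrected because it is an individual stopping rule in a first-in-human study and the correction is short. Confidence is moderate, because the reconciling reading is available though unwritten.

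The conclusion rests on two assumptions: that Table 17-4 is the scale for the bullet, as Section 6 indicates, and that a prompt response can fall within the 15-minute observation. The table does not define prompt. The documents give no expected rate of infusion reactions, so I claim no frequency.

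The effect on the analysis is small. A reader might infer that subjects stopped early drop out of the safety analysis, since Protocol Section 10.4.1 asks for the full dose. SAP Section 4.2 includes anyone given any amount, and SAP Section 11 records the change, so they stay in. The PK population is different: an AV-1 subject who is permanently stopped with a partial dose leaves it. With 6 AV-1 subjects per cohort, one such subject leaves 6 − 1 = 5 for that dose level unless replaced. No endpoint, planned sample size or analysis method changes.

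**What to change.** Replace the restart sentence in Protocol Section 8.6.2 so that it agrees with the mandatory rule, for example:

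*The infusion may be restarted only if the event is judged not to be an infusion-related reaction or is Grade 1 under Table 17-4; if it is Grade 2 or higher, the infusion will be permanently stopped.*

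The provision that "the infusion rate may be slowed from a rate of 250 mL/hour to a rate of 125 mL/hour for symptom management" can stay as it is. The conflict concerns resuming after a halt, and a grade limit on slowing would be a new clinical rule.

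If the sponsor in fact intends to allow restart after a promptly resolved Grade 2 reaction, the bullet should change instead, with the no-resume threshold moved to Grade 3 or recurrence. The documents do not show which was intended; the edit above follows the stricter text.

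The cost is a one-sentence protocol amendment, which needs IRB approval before use (Section 9.1). No new data and no SAP change are required. The downside is that any subject permanently stopped receives a partial dose, and an AV-1 subject is then lost to the PK population. Section 10.2 allows up to 8 replacements, but Section 5.2.2 leaves replacement to the Investigator's discretion in consultation with the Sponsor, so the loss may not be made good.
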